7.9.2 Handling of Schedule of Assessments of Safety Variables

For data obtained after the end of study treatment, the data obtained within + 2 days after the last dose is taken will be included in analysis.

(1) Physical examination, vital signs, laboratory test (hematology, biochemistry, urinalysis)

Time points defined in analysis	Reference date*	Acceptable time range
Screening	Day -28 to Day -1	Day -28 to Day -1
Baseline	Day 1	Day 1
Week 4 to Week 48**	Day $7 \times x + 1$	Day $(7 \times x - 6)$ to Day $(7 \times x + 8)$ and before drug administration on the visit day
Week 52	Day 365	Day 358 to Day 372
End of Week 12 (Week 12 or at early termination before Week 12)	Day 85	Day 2 to Day 92
End of Week 28 (Week 28 or at early termination before Week 28)	Day 197	Day 2 to Day 204
End of treatment (Week 52 or at early termination)	Day 365	Day 2 to Day 372

*: Day 1 represents the first day of study treatment. The day before is expressed as Day -1.

**: Represents the reference date and acceptable time range for Week x.

(2) Laboratory test (fasting lipid profile test)

Time points defined in analysis	Reference date*	Acceptable time range
Baseline	Day 1	Before drug administration on Day 1 and 8 hours after the last meal
Week 12	Day 85	Day 78 to Day 92
Week 28	Day 197	Day 190 to Day 204
Week 40	Day 281	Day 274 to Day 288
Week 52	Day 365	Day 358 to Day 372
End of Week 12 (Week 12 or at early termination before Week 12)	Day 85	Day 2 to Day 92
End of Week 28 (Week 28 or at early termination before Week 28)	Day 197	Day 2 to Day 204
End of treatment (Week 52 or at early termination)	Day 365	Day 2 to Day 372

*: Day 1 represents the first day of study treatment.

**: Represents the reference date and acceptable time range for Week x.

- CONFIDENTIAL -

(3) 12-lead ECG

Time points defined in analysis	Reference date*	Acceptable time range
Screening	Day -28 to Day -1	Day -28 to Day -1
Week 28	Day 197	Day 190 to Day 204
Week 52	Day 365	Day 358 to Day 372
End of Week 28 (Week 28 or at early termination before Week 28)	Day 197	Day 2 to Day 204
End of treatment (Week 52 or at early termination)	Day 365	Day 2 to Day 372

*: Day 1 represents the first day of study treatment. The day before is expressed as Day -1.

(4) Body weight

Time points defined in analysis	Reference date*	Acceptable time range
Screening	Day -28 to Day -1	Day -28 to Day -1
Week 12	Day 85	Day 78 to Day 92
Week 28	Day 197	Day 190 to Day 204
Week 40	Day 281	Day 274 to Day 288
Week 52	Day 365	Day 358 to Day 372
End of Week 12 (Week 12 or at early termination before Week 12)	Day 85	Day 2 to Day 92
End of Week 28 (Week 28 or at early termination before Week 28)	Day 197	Day 2 to Day 204
End of treatment (Week 52 or at early termination)	Day 365	Day 2 to Day 372

*: Day 1 represents the first day of study treatment. The day before is expressed as Day -1.

(5) QT assessment

Time points defined in analysis	Reference date	Acceptable time range
Baseline	Day 1	Day 1 Before the initiation of treatment with the study drug
Week 4 or Week 8 (before study drug administration)	Day 29 or Day 57	Before the initiation of treatment with the study drug on Reference date \pm 7
Week 4 or Week 8 (after study drug administration)	Day 29 or Day 57	2 hours post-dose (reference time, but within the range of 1 hour to 4 hours post-dose is acceptable) on Reference date \pm 7

- CONFIDENTIAL -

7.9.3 Handling of Schedule of Assessments of Pharmacodynamic Variables

(1) Biomarkers and lymphocyte subsets

Time points defined in analysis	Reference date*	Acceptable time range
Baseline	Day 1	Before drug administration on Day 1
Week 4 to Week 28**	Day $7 \times x + 1$	Day $(7 \times x - 6)$ to Day $(7 \times x + 8)$ and before drug administration on the visit day
Week 52	Day 365	Day 358 to Day 372
End of Week 12 (Week 12 or at early termination before Week 12)	Day 85	Day 2 to Day 92
End of Week 28 (Week 28 or at early termination before Week 28)	Day 197	Day 2 to Day 204
End of treatment (Week 52 or at early termination)	Day 365	Day 2 to Day 372

*: Day 1 represents the first day of study treatment. The day before is expressed as Day -1.

** : Represents the reference date and acceptable time range for Week x.

7.9.4 Handling of Schedule of Assessments of Pharmacokinetic Variables

(1) Trough concentration

Time points defined in analysis	Reference date*	Acceptable time range
Baseline	Day 1	Before drug administration on Day 1
Weeks 4, 8, 12, 20, 28, 40, and 52**	Day $7 \times x + 1$	Day $(7 \times x - 6)$ to Day $(7 \times x + 8)$ and within 19 to 29 hours between the time of treatment with the study drug before blood collection and the time of blood collection

*: Day 1 represents the first day of study treatment.

** : Represents the reference date and acceptable time range for Week x.

(2) Post-dose concentration

Time points defined in analysis	Reference date*	Acceptable time range
Week 4 or Week 8**	Day $7 \times x + 1$	Day $(7 \times x - 6)$ to Day $(7 \times x + 8)$ and within 1 to 4 hours between the time of treatment with the study drug before blood collection and the time of blood collection

*: Day 1 represents the first day of study treatment.

** : Represents the reference date and acceptable time range for Week x.

- CONFIDENTIAL -

8 OPERATIONAL AND ADMINISTRATIVE CONSIDERATIONS

8.1 Procedure for Clinical Study Quality Control

8.1.1 Data Collection

The investigator is responsible to ensure that all data in the eCRFs and queries are accurate and complete and that all entries are verifiable with source documents. These source documents should be appropriately maintained by the study center.

The investigator, sub-investigator, or collaborator will enter data collected using an Electronic Data Capture (EDC) system. The investigator, sub-investigator, or collaborator will enter the data, in principle within 5 working days from the creation of the data (date of visit by the subject, date of obtaining information, etc.).

In principle, the name of AE must be entered within 5 working days of the date of confirming its occurrence. The name of concomitant drug/therapy must also be entered within 5 working days of the awareness of its use. Other information to be entered in the eCRF must be entered immediately on receipt.

The monitor should verify the data in the eCRFs with source documents and confirm that there are no inconsistencies between them.

For screening failures, the minimum demographic data (sex, birth date, and informed consent date) and, if reason for screening failure is to be obtained, the screening failure log (SFL) will be collected.

Measurements of laboratory tests, pharmacodynamic parameters, and plasma drug concentrations will be performed by [REDACTED]. The Data Science Department of the sponsor will obtain the laboratory test results, pharmacodynamic measurements, and plasma drug concentration measurements in an electronic format from [REDACTED] at predefined intervals during the study.

The assessment of hand and foot radiography will be performed by [REDACTED]. The Data Science Department of the sponsor will obtain the assessment results in an electronic format from [REDACTED], at predefined intervals during the study.

Analysis of Central ECG will be performed by [REDACTED]. The Data Science Department of the sponsor will obtain the quality assured analysis data in an electronic format from [REDACTED] at predefined timing.

The central laboratory and [REDACTED] will provide the sponsor with a copy of the complete and clean data, together with the quality control report.

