Administration of ASP015K 100 mg BID had no effect on the pharmacokinetic profile of MTX in patients with RA or the MMF metabolites MPA and MPAG in healthy volunteers. ASP015K 60 mg and 100 mg BID did increase tacrolimus levels in whole blood following oral administration of tacrolimus 5 mg, but not when tacrolimus was administered as a 1 mg intravenous dose. Concomitant use of ASP015K elevated the plasma midazolam concentrations after a single oral dose of midazolam 3 mg. It also raised the plasma rosuvastatin levels following a single oral dose of rosuvastatin 10 mg. However, steady-state pharmacokinetics of ASP015K were not significantly impacted by MTX 15 to 25 mg, MMF 1 g, midazolam 3 mg, oral tacrolimus 5 mg, or intravenous tacrolimus 1 mg doses.

In Study 015K-CL-PS01 that enrolled patients with psoriasis, the administration of ASP015K 10 to 100 mg BID elevated ASP015K exposure (C_{max} , AUC_{last} , and AUC_{6h}) in a dose-dependent manner. The median t_{max} values were in the range of approximately 1.0 to 1.8 hours. STAT5 phosphorylation and JAK3 activity were inhibited in a dose-dependent

- CONFIDENTIAL -

manner. Although no consistent trends were noted for the absolute lymphocyte count, a slight dose-dependent decreasing trend was noted for the proportions and absolute counts of NK and B cells.

In Study 015K-CL-RAJ1 of Japanese patients with RA, matrix metalloproteinase 3 (MMP-3) levels decreased in a dose-dependent manner following the administration of ASP015K 25 to 150 mg QD. Although no consistent trends were noted for the absolute lymphocyte count, NK cell counts decreased and B cell counts increased in a dose-dependent manner.

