4.4 Blinding

4.4.1 Blinding Method

Treatment allocation to the ASP015K 100 mg, ASP015K 150 mg, or placebo groups is double-blinded. The ASP015K tablet 100 mg, ASP015K tablet 100 mg placebo, or ASP015K tablet 150 mg, ASP015K tablet 150 mg placebo are indistinguishable from each other in appearance, and the packaging for each treatment group (100 mg, 150 mg, and placebo) is also indistinguishable from that for other groups in appearance. The treatment code will only be known to the person responsible for assigning study drugs, person appointed at the

- CONFIDENTIAL -

institution performing measurements of plasma drug concentrations, persons in the Safety Control Division when necessary for Suspected Unexpected Serious Adverse Reaction (SUSAR) handling, and independent Data and Safety Monitoring Board (DSMB).

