5.3.2 Pharmacodynamic Assessments

Blood samples will be collected at baseline and on days specified in the Schedule of Assessments. At the study visit points where blood sample collection for PK assessment is performed, sample collection for PD assessment will be performed before study drug administration and at the same time as that for the sampling for PK assessment. These measurements will be performed at the central laboratory (), and the results will be reported to the sponsor and the study center after the breaking of the treatment code.

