5.6 Test Drug Concentration

The plasma concentrations of ASP015K will be measured in the samples collected at the time points in Table 1 Schedule of Assessments. The concentrations of ASP015K metabolites H1, H2, and H4 will be measured if necessary.

In the placebo group, the concentrations of samples collected during the period of the administration of placebo will not be measured, but the concentration of samples collected after switching to ASP015K 100 mg or ASP015K 150 mg will be measured. The concentration of the sample collected on the day of the visit for switching will be measured as baseline.

The subject registration center will provide information on study drug assignment to the institution performing measurements of drug concentrations.

Whether to measure the concentrations of samples from the placebo group depends on switching to ASP015K 100 mg or ASP015K 150 mg; thus, the subject registration center will provide the institution performing measurements of drug concentrations with information on whether subjects switched to ASP015K 100 mg or ASP015K 150 mg at Week 12. After obtaining information on switching, the institution performing measurements of drug concentrations will measure the drug concentrations of samples of subjects in the placebo group who switched to ASP015K 100 mg or ASP015K 150 mg.

Concentration measurements will be performed by [REDACTED] using a validated, established LC-MS/MS method [Test No.: [REDACTED] (ASP015K, H2), [REDACTED] (H4), [REDACTED] (H1)]. The lower limit of quantification is 0.25 ng/mL. Blood samples for drug concentration (2 mL/sample) will be collected into a 2 mL vacutainer tube containing ethylenediamine-tetra-acetic acid (K₃EDTA-3K). See the written explanation of testing procedure enclosed in the clinical laboratory testing kit for descriptions of the procedure for sampling blood and storing and shipping the blood samples. The central laboratory ([REDACTED]) will not report the results of determinations to the investigator, sub-investigator, sponsor, or other third parties until the breaking of the treatment code.

- CONFIDENTIAL -

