5.7 Other Measurements, Assessments, or Methods

5.7.1 Pharmacodynamic Measurements

In this study, the following will be measured as part of the pharmacodynamic evaluation: biomarkers of bone or cartilage metabolism and lymphocyte subsets (see Section 5.3.2.2 Biomarkers for Efficacy and Safety Assessments).

Blood samples for biomarkers of bone or cartilage metabolism will be collected in a 2 mL sampling tube containing EDTA-2Na, and samples for lymphocyte subsets will be collected in a 2 mL vacutainer tube containing EDTA-2K. See the written explanation of testing procedure enclosed in the clinical laboratory testing kit for descriptions of the procedure for sampling blood and storing and shipping the blood samples.

The central laboratory ([REDACTED]) will not report the results to the investigator, sub-investigator, sponsor, or other third parties until the breaking of the treatment code.

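### Protocol 8.1.1 sends plasma concentration and PD results to the sponsor during the study, although 5.3.2, 5.6 and 5.7.1 withhold them until code break; the concentration files could unblind sponsor data staff to active versus placebo.

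*Protocol*

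**What the plan says.** Protocol 8.1.1 (Data Collection) describes the transfer: "The Data Science Department of the sponsor will obtain the laboratory test results, pharmacodynamic measurements, and plasma drug concentration measurements in an electronic format". The sentence goes on to give the timing: "at predefined intervals during the study".

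Three other sections set the opposite rule for parts of these data:

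- Protocol 5.6, on plasma concentrations: the laboratory "will not report the results of determinations to the investigator, sub-investigator, sponsor, or other third parties until the breaking of the treatment code".
- Protocol 5.7.1, on PD measurements: the laboratory "will not report the results to the investigator, sub-investigator, sponsor, or other third parties until the breaking of the treatment code".
- Protocol 5.3.2, also on PD: "the results will be reported to the sponsor and the study center after the breaking of the treatment code".

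Protocol 5.6 adds, for the placebo group, that "the concentrations of samples collected during the period of the administration of placebo will not be measured". Samples from the switch visit onward are measured.

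Protocol 4.4.1 gives a closed list of people with access to allocation. It begins "The treatment code will only be known to the person responsible for assigning study drugs" and adds a person at the concentration laboratory, Safety Control staff where a SUSAR requires it, and the DSMB. The Data Science Department is not named.

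**The concern.** 8.1.1 is specific: it names the recipient, the data types, the format and the timing. A data-transfer agreement drafted from it would deliver concentration and PD files to the sponsor before unblinding. One drafted from 5.3.2, 5.6 and 5.7.1 would not.

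The concentration files matter most, because the decision to assay a sample depends on allocation. A blinded reader would not need to interpret a single value; the presence or absence of a result is informative. At stake is the sponsor's blind in a double-blind confirmatory trial during a period when some analysis decisions are still open. Protocol 7.2 gives the Case Review Meeting the final say on inclusion in the analyses. Protocol 7.9 has it settle the handling of missing data, outliers and visit windows before code break.

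**Working it through.** No formula applies. The check sets the passages side by side and then asks what each file could reveal.

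**Step 1: is there a true conflict?**

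| Data | 8.1.1 | Other section |
|---|---|---|
| Plasma concentrations | To sponsor during the study | 5.6: not to sponsor before code break |
| PD results | To sponsor during the study | 5.3.2 and 5.7.1: not to sponsor before code break |
| Other laboratory results | To sponsor during the study | No hold stated |

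One section covers concentrations and two cover PD. All three name the sponsor, so the conflict does not depend on which laboratory is meant, although laboratory names are redacted. Only the PK and PD parts of 8.1.1 conflict.

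**Step 2: does anything resolve it?** Neither document states an order of precedence, masked identifiers, a restricted recipient or a delayed transfer for these files. The SAP (6.3 and 7.6) refers PK to a separate plan. The timing in 8.1.1 does not look accidental either: for Central ECG the section promises transfer at a predefined time without placing it within the study.

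**Step 3: what would concentration files show?** Protocol 4.4.3 gives the concentration laboratory a copy of the randomization list, and 5.6 has it told which placebo subjects switched at Week 12. Its output therefore reflects allocation. Combining Table 1 with 5.6:

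- Active groups: trough samples measured from baseline, then at Weeks 4, 8, 12, 20, 28, 40 and 52.
- Placebo, switched at Week 12: nothing measured before the Week 12 sample, which serves as that subject's baseline.
- Placebo, switched at Week 28: nothing measured before the Week 28 sample.

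With 170 subjects per group (Protocol 7.1), 2 × 170 = 340 would have records from baseline and 510 − 340 = 170 would have none until they switch. The pattern separates active from placebo and dates the switch. Both active groups have the same sampling schedule, so record presence does not separate 100 mg from 150 mg.

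**Step 4: what would PD files show?** Much less. In the Phase IIb study, MMP-3 "levels decreased in a dose-dependent manner following the administration of ASP015K 25 to 150 mg QD" (Protocol 1.2.2.2). That is a group trend and only a hint for an individual. Protocol Appendix 2 runs MMP-3 with the biochemistry tests, so it could travel in routine laboratory files even if a separate PD file were held back.

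**Step 5: where could the knowledge act?** The Data Science Department coordinates data management (Protocol 8.1.5). The planned study period ends in January 2018 (Synopsis) and SAP version 1.00 is dated 18 January 2018, so most in-study transfers would precede the final SAP and the decisions left to the Case Review Meeting.

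**The case against.** A reader might infer that this undermines both primary endpoints directly. The documents do not support that. ACR20 components come from site investigators, subjects and central-laboratory CRP (Protocol 5.3.1), and 8.1.1 sends no PK or PD data to sites. mTSS is scored by a third-party institution from images with subject information masked (5.3.1.9). The full analysis set is all randomized and dosed subjects (Protocol 7.2.1, SAP 5.1). The primary tests and imputation rules are stated in Protocol 7.4.1.1. The per-protocol sets serve only to assess robustness, and SAP 7.11.2 keeps every value, so no discretion over outliers remains. All of this stands and removes the claim of direct endpoint bias.

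It can also be said that the three specific holds and the closed list in 4.4.1 make the intent plain, that separate data-management procedures may already mask or delay these files, and that nothing links data-management staff to the Case Review Meeting decisions. SAP section 1 has the analysis coordinated by a biostatistician from another named unit. This also stands in part: actual unblinding is not shown, the content of the transferred files is not described, and the link from recipient to decision-maker is an inference. It does not remove the contradiction. No text says the specific sections prevail, and 8.1.1 is where a reader looks for transfer rules.

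**Conclusion.** The contradiction is certain on the text. Following 8.1.1 as written could let sponsor staff outside the 4.4.1 list distinguish about 340 active from about 170 placebo subjects and see when placebo subjects switch. This assumes that enrolment meets the plan and that the files carry subject identifiers and let a reader see which samples have no result. The stronger reading, that the full three-arm allocation is revealed, is not supported: record presence does not distinguish the two doses, and PD data only hint at treatment.

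The risk is to the sponsor's blind and to the judgments left open before code break in Protocol 7.2 and 7.9. It is not a demonstrated bias in either primary endpoint. It merits correction because the protocol's own blinding rules point one way and a single sentence points the other.

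**What to change.** Amend Protocol 8.1.1 so that in-study transfers to the sponsor exclude plasma concentrations and all PD results: VEGF, lymphocyte subsets, and MMP-3 even though it is run with biochemistry. State that these files reach the sponsor only after code break, as 5.3.2, 5.6 and 5.7.1 already require, and align the data-transfer agreement. All other routine laboratory data, including CRP, anti-CCP antibody and rheumatoid factor, continue as planned; the last two are needed for inclusion criterion 10.

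Early release to a firewalled sponsor group is not a simple alternative. It would conflict with the same three sections unless they and the 4.4.1 list were amended too.

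If any such file was sent before code break, record what was sent, when and to whom.

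The cost is one sentence in the protocol, a matching change to the transfer agreement, and later cleaning of PK and PD data. No analysis or sample size changes.

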8.1.2 Specification of Source Documents

Source data must be available at the study center to document the existence of the study subjects and substantiate the integrity of study data collected. Source data must include the original documents relating to the study as well as those relating to the medical treatment and medical history of the subject.

- CONFIDENTIAL -

The following information should be included in the source medical records:

- Demographic data (birth date, sex, height, and body weight)
- Inclusion and exclusion criteria details
- Participation in study and signed and dated informed consent forms
- Visit dates
- Medical history and physical examination details
- Key efficacy and safety data
- AEs and symptomatic treatment
- The results of the relevant examination (e.g., ECG charts, radiographic data, etc.)
- Laboratory test slips/reports
- Dispensing and return of study drug details
- Reason for premature discontinuation
- Records of RA diagnosis and evaluation, patient questionnaires (e.g., HAQ-DI, SF-36v2[®], WPAI)
- Subject questionnaire for CPK monitoring
- Herpes Zoster (shingles) Worksheet

If the following data are not included in medical records, the entries in the eCRFs are treated as source data:

- Dates of AE occurrence and resolution, its severity, seriousness, outcome, causality to the study drug, and rationale for the causality
- Route of administration, treatment dates, and reason of use for previous and concomitant drugs
- Type, treatment dates, and reason of use for previous and concomitant therapies
- Presence or absence of abnormal 12-lead ECG readings, abnormal findings
- Date, reason, and background/details for discontinuation
- Other comments

